**Injectable Extended-Release Buprenorphine in A Correctional Setting: Phase 2**  
**IRB RESEARCH PROTOCOL – 10/9/23**  
**PI: [name] MPH MBA**

**RESEARCH OBJECTIVES:**

- (1) To better understand the perceived benefits and risks associated with injectable buprenorphine (“Sublocade”) in a correctional setting
- (2) To better understand the facilitators and barriers of Medication for Addiction Treatment (MAT) programs in a correctional setting and if/how injectable buprenorphine can affect implementation
- (3) To identify specific groups of individuals within a correctional setting that may benefit from injectable buprenorphine

**Background**

The opioid overdose epidemic continues to escalate, further exacerbated by the Covid-19 pandemic, and incarcerated individuals are a particularly vulnerable group for death. One-third of people with opioid use disorder (OUD) have encountered the criminal justice (CJ) system in the past year. Upon release from prison, individuals have a 129 times greater risk of opioid overdose death than the general population. **Nearly half of fatal opioid overdoses occur in people with CJ involvement.**

When initiated in a correctional setting (i.e., a jail or prison), medications for OUD (MOUD), such as **buprenorphine, can significantly increase treatment engagement in the community and reduce mortality by 50%.** Despite the robust evidence on MOUD effectiveness, <10% of incarcerated individuals with OUD receive medication. Crucial individual- and structural-level barriers including stigma, diversion, resource needs for daily oversight, and cost, have constrained MOUD uptake in jails and prisons.

**Extended-release buprenorphine (XR-B), a novel MOUD modality, can address many barriers to implementation.** XR-B is a monthly injectable MOUD that can decrease burden on correctional staff, reduce medication diversion, increase adherence, and offer individuals more time for linkage to post-release care in the community. XR-B has demonstrated efficacy in community settings but **there is no published data on the feasibility, acceptability, and implementation of XR-B initiation in a correctional setting.**

This proposal seeks to fill this gap. The overall research objective of this work is to evaluate the initiation of XR-B in a correctional facility. The central hypothesis is that XR-B is a feasible, acceptable, and effective alternative to treatment-as-usual sublingual buprenorphine (SL-B).

Stigma, racial inequality, and mass incarceration decrease MOUD access to CJ-involved individuals compared to the general population. To better understand this multi-level disparity, the proposed work will identify barriers and facilitators to MOUD treatment across multiple stakeholders in the carceral system. By understanding the experiences and needs of a marginalized population, and identifying concerns from other key stakeholders, this proposed work can enhance future uptake of lifesaving MOUD, provide data to inform future trials, and support patient-centered treatment considerations across all CJ facilities.

**The Rhode Island Department of Corrections (RIDOC) is an ideal study site for this proposal.** RIDOC was the first statewide CJ institution to create a comprehensive program for MOUD and is one of few facilities to have familiarity with XR-B initiations in a small non-research sample.

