## **Purpose of Research Project**

This proposed research seeks to identify multi-level barriers and facilitators to the implementation of XR-B. This study initiates a mixed-methods multi-level process evaluation that will explore perspectives from individual and organizational stakeholders before a planned clinical trial to measure the effectiveness of XR-B in a CJ setting (a future IRB application: Phase 3).

The proposed study will enhance the understanding of MOUD treatments in correctional settings especially during transition to the community. This will include interviews with incarcerated individuals with diagnosed opioid use disorder and organizational stakeholders (e.g., medical staff, Wardens, leadership) who are willing and able to participate in interviews and/or surveys to assess their views on MAT operations. All interviews are guided by a structured interview guide based on prior research and implementation frameworks, in collaboration with the COBRE on Opioids and Overdose Community Engaged Research Core.

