## **SUBJECT RECRUITMENT:**

### **Recruitment Population.**

***Incarcerated individuals*** will be recruited across RIDOC facility during the required group sessions for treatment; this is consistent with previous NIH-funded studies at RIDOC. The interviews will be described and participants will be able to sign up confidentially. Participants who are eligible for MOUD but decide not to pursue treatment will still be interviewed to provide better understanding of the key factors that drive program participation. These individuals can be recruited through routine clinical care by addiction medicine providers. Every precaution will be taken to ensure confidentiality and protection of all participants.

***Organizational stakeholders*** (clinicians, Wardens, leadership and/or other staff) will be recruited through snowball sampling. I will individually approach leaders of each facility to recruit correctional individuals interested in participating and will also allow participants to confidentially sign up at administrative meetings related to Medication for Addiction Treatment (MAT).

**Interview Sample Size.** Each interview group (i.e., Incarcerated Individuals and Organizational Stakeholders) will recruit at least 6 - 12 individuals until analysis reflects saturation. Incarcerated persons will be stratified by on injectable treatment or not and so may have 18 - 24 interviewees total. In implementation science, this number of interviews per stakeholder group should ensure saturation based on previous literature. All individuals will be over the age of 18. Diverse participants according to race, gender, age, type of MOUD, and facility of residence will purposively be recruited. Women make up 15% of incarcerated individuals at RIDOC and will be oversampled to include their important perspective. Individuals will receive renumeration in their commissary account, similar to previous RIDOC studies.

**Survey Sample Size.** We hope to have ~12 surveys completed by organizational stakeholders during provider meetings, Medication for Addiction Treatment (MAT) meetings, or during research interviews with stakeholders. Surveys take under 5 minutes to complete. Additional compensation will not be offered. All survey data is anonymous.

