**Interview Guide.** An open-ended interview guide has been developed based on existing literature and with input from the COBRE Community Engagement Research Core. *The core qualitative research question* will be: What are the barriers and facilitators to successful uptake of XR-B? As common practice in implementation research, the interviews will be shaped by a conceptual framework, in this case, iPARIHS. A preliminary interview guide is attached though will be revised in an iterative process based on emerging themes. As described in the guide, questions will not be verbatim but ensure all content areas are discussed. Interviews with patients will have greater emphasis on Recipient and Innovation domains, while interviews with other stakeholders will focus on Context and Facilitation domains.

**Surveys.** Copies of (1) Organizational Readiness for Implementing Change (ORIC), (2) Staff Attitudes Toward MOUD (SATM), and (3) Implementation Outcome Measures are attached. Paper forms will be completed by organizational stakeholders (without name or other PHI) and will be entered into REDCap secure software to record results. Original copies of survey sheets will be locked in the PI's office.

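### Does a central hypothesis that includes effectiveness require a change to this interview-and-survey study?

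*Protocol*

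**What the plan says.** The Background of the Protocol names an evidence gap: "there is no published data on the feasibility, acceptability, and implementation of XR-B initiation in a correctional setting". It says the proposal sets out to fill that gap and continues: "The overall research objective of this work is to evaluate the initiation of XR-B in a correctional facility". The next sentence gives the only hypothesis in the document: "The central hypothesis is that XR-B is a feasible, acceptable, and effective alternative to treatment-as-usual sublingual buprenorphine (SL-B".

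Purpose of Research Project describes the study itself: "This proposed research seeks to identify multi-level barriers and facilitators to the implementation of XR-B". It is a mixed-methods process evaluation carried out "before a planned clinical trial to measure the effectiveness of XR-B in a CJ setting (a future IRB application: Phase 3".

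The first of the three Research Objectives is "To better understand the perceived benefits and risks associated with injectable buprenorphine". The second concerns facilitators and barriers of treatment programmes. The third is to identify groups that may benefit. Interview Guide sets the core question: "What are the barriers and facilitators to successful uptake of XR-B". For sampling, Interview Sample Size says: "Incarcerated persons will be stratified by on injectable treatment or not".

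**The concern.** A central hypothesis normally tells the reader what the study will be able to support or refute. This one has three parts (feasible, acceptable, effective) and names a comparator, SL-B. It follows directly on a sentence about the objective of this work, and nothing marks it as the hypothesis of a larger programme. The effectiveness part has nothing behind it in the data to be collected: there is no retention, opioid use, overdose or post-release linkage outcome, no treatment assignment and no SL-B group.

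The worry is one of interpretation. If favourable opinions from a small, purposively chosen sample were reported as supporting the stated hypothesis, they could be taken as evidence of effectiveness before the trial meant to provide it. The non-injectable stratum could likewise be mistaken for an SL-B control group, although it includes other medications and people who declined treatment.

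**Working it through.** No arithmetic applies. The Protocol gives no error rate, power, effect size, margin or follow-up time, and the interview numbers rest on saturation. The useful check is whether any working part of the study depends on the word *effective*.

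| Element (Protocol section) | What it specifies | Depends on effectiveness or on an SL-B comparison? |
|---|---|---|
| Research Objectives | Perceived benefits and risks; facilitators and barriers; groups that may benefit | No |
| Purpose of Research Project | Barriers and facilitators to implementation; effectiveness left to a later trial | No; it excludes it |
| Interview Sample Size | At least 6 to 12 per interview group, until saturation; possibly 18 to 24 in total once incarcerated participants are split | No |
| Stratification (same section) | On injectable treatment or not | No; never called a comparator |
| Surveys | Three questionnaires on readiness, attitudes and implementation, completed by organizational stakeholders | No |
| Interview Guide | Barriers and facilitators to uptake | No |
| Data Collection and Analysis | Directed content and thematic coding; no effect on routine care | No |

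Three observations follow.

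1. **Count.** Of the three components of the hypothesis, two (feasible, acceptable) can be explored descriptively through the interviews and the implementation outcome measures. One (effective) has 0 endpoints. Defined SL-B groups also number 0. The factual basis of the concern is therefore correct.

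2. **Where the mismatch sits.** The gap named shortly before the hypothesis covers feasibility, acceptability and implementation, and does not mention effectiveness. Purpose of Research Project then assigns effectiveness to a separate future application. The hypothesis sentence is out of step with text on both sides of it, while the sections that govern conduct agree with one another. The third objective, on groups that may benefit, comes closest to an effect claim. The only data available for it are interviews and staff questionnaires, so it too is answered in terms of perception.

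3. **What the stratum is for.** Under Recruitment Population, people eligible for medication who decline it are interviewed on purpose, to understand what drives participation, and Interview Sample Size seeks diversity by type of medication. Mixing treatments on the non-injectable side serves that aim. A missing SL-B minimum would be a defect only if a comparison with SL-B were planned, and none is.

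If the sentence were reworded, or *effective* removed, the same people would be interviewed with the same guide, the same questionnaires would be completed and the same coding would be done. The difference in results is nil.

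**The case for a change.** The best case for a change is that this is the document's only hypothesis, that its immediate context ties it to this work, and that correcting it costs a few words. A statistical analysis plan could not rescue it, because no plan can analyse outcomes that are not collected. The participants are prisoners, whom the Protocol itself treats as vulnerable, and the bodies reviewing the study should see a hypothesis that matches what those participants contribute to. If a qualitative study needs no testable hypothesis, it should not state a comparative one.

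Most of this stands as a comment on drafting. The sentence is inaccurate for this phase, and the Background does not say that it belongs to a wider programme. Two parts of the argument do not stand. The first is the feared misreporting: the Protocol contains no reporting or decision rule that would turn opinions into a claim of effectiveness, its planned analytic output is themes on barriers and facilitators, and it names the later trial as the place where effectiveness will be measured. The second is the complaint about the comparator, which applies the standards of a controlled trial to an interview sampling frame. Adding a named SL-B stratum would be a sampling preference, and it would not make effectiveness testable.

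**Conclusion.** The concern is right on the facts, but no change to the plan follows from it. The Background overstates what this phase can show by one of three hypothesis components. Purpose of Research Project limits that overstatement, and no objective, sample size, stratum, measure or analysis relies on it. Followed as written, the plan yields an account of barriers, facilitators and perceptions, which is what the objectives ask for.

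This rests on two assumptions. The first is that the analysis stays as described, thematic and without a contrast between treatments. The second is that those writing up the results respect the Protocol's own assignment of effectiveness to Phase 3. Both are the natural reading of the document. Marking the hypothesis as the programme's would be a harmless tidy-up at any future revision, but it is an editorial matter and would alter no result.

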**Theoretical Goals**

The proposed research offers a critical opportunity to leverage RIDOC institutional support and experience to assess implementation of XR-B initiation through an implementation science framework.

## **Purpose of Research Project**

This proposed research seeks to identify multi-level barriers and facilitators to the implementation of XR-B. This study initiates a mixed-methods multi-level process evaluation that will explore perspectives from individual and organizational stakeholders before a planned clinical trial to measure the effectiveness of XR-B in a CJ setting (a future IRB application: Phase 3).

The proposed study will enhance the understanding of MOUD treatments in correctional settings especially during transition to the community. This will include interviews with incarcerated individuals with diagnosed opioid use disorder and organizational stakeholders (e.g., medical staff, Wardens, leadership) who are willing and able to participate in interviews and/or surveys to assess their views on MAT operations. All interviews are guided by a structured interview guide based on prior research and implementation frameworks, in collaboration with the COBRE on Opioids and Overdose Community Engaged Research Core.

## **SUBJECT RECRUITMENT:**

### **Recruitment Population.**

***Incarcerated individuals*** will be recruited across RIDOC facility during the required group sessions for treatment; this is consistent with previous NIH-funded studies at RIDOC. The interviews will be described and participants will be able to sign up confidentially. Participants who are eligible for MOUD but decide not to pursue treatment will still be interviewed to provide better understanding of the key factors that drive program participation. These individuals can be recruited through routine clinical care by addiction medicine providers. Every precaution will be taken to ensure confidentiality and protection of all participants.

***Organizational stakeholders*** (clinicians, Wardens, leadership and/or other staff) will be recruited through snowball sampling. I will individually approach leaders of each facility to recruit correctional individuals interested in participating and will also allow participants to confidentially sign up at administrative meetings related to Medication for Addiction Treatment (MAT).

**Interview Sample Size.** Each interview group (i.e., Incarcerated Individuals and Organizational Stakeholders) will recruit at least 6 - 12 individuals until analysis reflects saturation. Incarcerated persons will be stratified by on injectable treatment or not and so may have 18 - 24 interviewees total. In implementation science, this number of interviews per stakeholder group should ensure saturation based on previous literature. All individuals will be over the age of 18. Diverse participants according to race, gender, age, type of MOUD, and facility of residence will purposively be recruited. Women make up 15% of incarcerated individuals at RIDOC and will be oversampled to include their important perspective. Individuals will receive renumeration in their commissary account, similar to previous RIDOC studies.

**Survey Sample Size.** We hope to have ~12 surveys completed by organizational stakeholders during provider meetings, Medication for Addiction Treatment (MAT) meetings, or during research interviews with stakeholders. Surveys take under 5 minutes to complete. Additional compensation will not be offered. All survey data is anonymous.

**Recruitment Process.** For incarcerated individuals, a member of the research staff will approach group therapy sessions for individuals enrolled in the Medication for Addiction Treatment (MAT) program at the Rhode Island Department of Corrections. They will explain the study, the time requirement (60 - 90 minutes) and the compensation (\$25) for interviews and offer the opportunity to confidentially sign up for the study. Addiction providers will also be able to sign up interested participants during routine clinical care.

Organizational stakeholders will be recruited through snowball sampling and/or administrative meetings. I will individually approach leaders of each facility to recruit correctional individuals interested in participating (in either survey completion and/or in-depth interviews) and will also allow participants to confidentially sign up at administrative meetings related to Medication for Addiction Treatment (MAT).

All recruitment and tracking will be captured through a HIPAA-secure server: REDCap.

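### Does the interview plan need a minimum number of people who decline MOUD, and a corrected total in place of 18–24?

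*Protocol*

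**What the plan says.** All the relevant text is in the Protocol under Subject Recruitment.

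- **Size and stopping.** "Each interview group (i.e., Incarcerated Individuals and Organizational Stakeholders) will recruit at least 6 - 12 individuals until analysis reflects saturation". The split follows: "Incarcerated persons will be stratified by on injectable treatment or not and so may have 18 - 24 interviewees total". The support offered is that "this number of interviews per stakeholder group should ensure saturation based on previous literature". The In-depth Interviews and Study End Date entries also make saturation the stopping point.
- **Decliners.** Those who qualify for medication "but decide not to pursue treatment will still be interviewed to provide better understanding of the key factors that drive program participation". Of their route the Protocol says: "These individuals can be recruited through routine clinical care by addiction medicine providers".
- **Main route.** Incarcerated individuals "will be recruited across RIDOC facility during the required group sessions for treatment". Recruitment Process specifies that "a member of the research staff will approach group therapy sessions for individuals enrolled in the Medication for Addiction Treatment (MAT) program", and adds: "Addiction providers will also be able to sign up interested participants during routine clinical care".
- **Purposive factors.** Race, gender, age, type of MOUD and facility. Women are to be oversampled, with no number attached.

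**The concern.** The Protocol gives a specific reason for hearing from people who stay out of treatment, but nothing in the sampling plan is sized for them. They share the stratum not on injectable treatment with people on other MOUD. Declining is not among the purposive factors. The group sessions are for people already enrolled in the MAT program, so decliners depend on provider referral. Saturation is stated by interview group or in general. A sample drawn mostly from MAT sessions could seem saturated on enrollees' themes while decliners' themes are barely heard, and closing with one or two decliners would still comply. The study would then say little about why eligible people do not join, which bears on the objective concerning barriers and facilitators of MAT programs.

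The range adds to the doubt. It is presented as following from the stratification, yet no arithmetic is shown and the total is not defined. A reader may ask whether stakeholders are counted in it and how many interviews each stratum should have.

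**Working it through.** **1. Can 18–24 be reproduced?** Inputs: 6–12 per group, two groups, and two strata among incarcerated persons, all from Interview Sample Size. No power formula applies, because the study is sized by saturation.

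Uniform application, cells × (6–12):

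| Cells | Reading | Result |
|---|---|---|
| 1 | incarcerated, unstratified | 6–12 |
| 2 | two incarcerated strata | 12–24 |
| 3 | two strata plus stakeholders | 18–36 |

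Two cells match only the upper end and three only the lower, so the figure is not a uniform multiple. Other allocations give it exactly:

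- incarcerated only, 9–12 in each of two strata: 2 × 9 = 18, 2 × 12 = 24;
- incarcerated only, one stratum of 12 and one of 6–12: 12 + 6 = 18, 12 + 12 = 24;
- everyone, two strata of 6 plus 6–12 stakeholders: 2 × 6 + 6 = 18, 2 × 6 + 12 = 24.

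Arithmetic alone does not settle the scope. Grammar favors incarcerated persons, who are the subject of the sentence. Stakeholders would then be additional: (18–24) + (6–12) = 24–36 in all. On that reading 18–24 lies inside the uniform range of 12–24. Replacing it with 12–24 would lower the planned minimum from 18 to 12 for no stated reason.

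**2. Could decliners be missed?** The Protocol gives no share of decliners in the stratum not on injectable treatment, so any share is an assumption. If recruits were independent random draws, the chance of having none is (1 − s)^n:

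| Assumed share s | n = 6 | n = 12 |
|---|---|---|
| 10% | 0.9^6 = 53% | 0.9^12 = 28% |
| 20% | 0.8^6 = 26% | 0.8^12 = 7% |
| 33% | 0.67^6 = 9% | 0.67^12 = 0.8% |

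These figures do not describe the plan. Interviewing decliners is a commitment, so closing with none would breach the Protocol, and they are referred by providers rather than drawn at random.

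**3. How much would a few decliners reveal?** The chance of hearing a theme at least once is 1 − (1 − p)^n, with prevalence p assumed:

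| Assumed p | n = 1 | n = 2 | n = 6 |
|---|---|---|---|
| 20% | 20% | 36% | 74% |
| 30% | 30% | 51% | 88% |
| 50% | 50% | 75% | 98% |

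More interviews hear more themes, as in any subgroup. The table does not identify a required number, and hearing a theme once is not saturation.

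**4. What would a minimum cost?** Take six, borrowed from the lower end of the group figure; the Protocol sets none for decliners. If none would otherwise be recruited, incarcerated interviews become (18–24) + 6 = 24–30, and the study total (24–30) + (6–12) = 30–42. Direct cost: 6 × $25 = $150 and 6 × 60–90 minutes = 6–9 hours, plus transcription and double coding. If saturation among decliners were also required, six would no longer be a ceiling.

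**The case for a change.** The best case for a change is that the commitment to interview decliners has no sampling rule behind it. Number, stratum, purposive factors, main route and stopping rule all pass them by. Recruitment numbers belong in this paragraph rather than in an analysis plan, and a minimum is compatible with saturation sampling, since the Protocol already sets one per group. A sentence or two would cost little.

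The description of the text stands: no number is set, and one or two decliners would comply. The consequence is weaker.

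- The core question in the Interview Guide section is uptake of the extended-release injection. The contrast closest to it is on versus not on the injectable, which is the contrast stratified. People in MAT but not on the injectable are reached through the group sessions.
- Barriers to MAT more broadly are also informed by stakeholders and enrolled participants. No comparison is defined for decliners.
- The permissive wording describes the route, not whether decliners are interviewed. Provider sign-up is repeated in Recruitment Process.
- The Protocol manages diversity purposively and without subgroup quotas; even the oversampled women have no number.
- The debrief after each interview and the iterative analysis let the team see that a perspective is thin and keep recruiting.

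**Conclusion.** No change follows. The first part is a gap that the research team can fill during recruitment: decliners must be interviewed, the provider route exists, and the sample is open-ended. The second part is an unexplained planning range, not a shown arithmetic error. It is feasible, reads most naturally as incarcerated persons only (24–36 with stakeholders), and feeds no estimate, test or stopping boundary.

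A decliner quota would mean up to six more interviews, or an open number if tied to saturation, in a group that may be slow to recruit, with no stated target currently missed. The number would be a preference about qualitative design rather than a correction.

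This rests on two assumptions: that the team honors the commitment to interview decliners, and that it considers them when judging saturation. If only one or two are reached, findings on why people decline are exploratory. That is a limit on interpretation, visible once the number interviewed is reported.
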